#### **Objectives:**

**Primary:** The primary objective of this study is to assess the safety of single infusions with the RePlasTM FDP product at increasing fixed doses of either 1 unit (approximately 270 mL), 2 units (approximately 540 mL), or 3 units (approximately 810 mL) in normal healthy subjects. In the 2 lower dose cohorts, safety will also be assessed in terms of the type of autologous plasma used as the starting material in the manufacture of the investigational product:

- RePlasTM FDP product manufactured from autologous FFP derived from whole blood (WB) donations where Citrate Phosphate Dextrose (CPD) is the anticoagulant, or RePlasTM FDP-CPD; and
- RePlasTM FDP product manufactured from autologous FFP collected during plasmapheresis where Acid Citrate Dextrose (ACD) is the anticoagulant, or RePlasTM FDP-ACD.

The highest dose cohort will receive FDP manufactured only from FFP collected by plasmapheresis (FDP-ACD). Conclusions on whether the study meets its safety objectives will be based only on treatment emergent adverse events (TEAEs). TEAEs are adverse events (AEs) that occur after administration of the study treatment, plasma infusion, has begun. AEs occurring prior to treatment (e.g., AEs that occur during autologous plasma collection) will not be considered relevant to the study's objectives.

Secondary: The secondary objectives are to:

Assess the safety of a fixed-dose infusion of 3 FDP units (approximately 810 mL) in
comparison to infusion with the same dose of autologous FFP collected during
plasmapheresis; and

Determine if the changes in specific coagulation factors, hematology, and chemistry values
are similar within clinically meaningful levels after infusion of either 3 units of autologous
FDP or FFP.

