#### 6. TRIAL OBJECTIVES AND PURPOSE

## 6.1. Primary Objective

The primary objective of this study is to assess the safety of single infusions with the RePlasTM FDP product at increasing fixed doses of either 1 unit (approximately 270 mL), 2 units (approximately 540 mL), or 3 units (approximately 810 mL) in normal healthy subjects. In the 2 lower dose cohorts, safety will also be assessed in terms of the type of autologous plasma used as the starting material in the manufacture of the investigational product:

- FDP derived from WB where CPD was used as the anticoagulant, or FDP-CPD; and
- FDP collected by plasmapheresis where ACD was used as the anticoagulant, or FDP-ACD.

The highest dose cohort will receive FDP manufactured only from FFP collected by plasmapheresis (FDP-ACD). Conclusions on whether the study meets its safety objectives will be based only on treatment emergent adverse events (TEAEs). These are adverse events (AEs) that occur after treatment (plasma infusion) has begun and throughout the study's post-infusion follow-up period.

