2. SAFETY

The safety of infusion with the experimental product will be determined by observation of treatment emergent adverse events (TEAEs), defined as only AEs that occur after starting the trial infusion administration. In addition to TEAEs, safety will be evaluated based on the occurrence of SAEs, suspected unexpected serious adverse reactions (SUSARs), and deaths. Safety assessment in Cohorts 1 and 2 subjects will examine the cohort-specific product infusion dose and the specific FDP product type infused (e.g., FDP-CPD or FDP-ACD). The safety assessment performed in Cohort 3 subjects will assess treatment with FDP at the highest fixed infusion dose (approximately 810 mL) and compare, within the same subject, the treatment safety of FDP versus FFP at the equivalent dose.

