4.2.2 Safety Populations

The three subject populations for assessing safety are defined as those who:

- Receive any volume of infused product; (i.e., In Cohort 3 subjects this includes those who received a partial dose at either Infusion Visit) (**S1**);
- Receive the full infusion dose and have at least one outcome measure (**S2**); and
- Receive the full infusion dose and can be fully evaluated because in: (**S3**, or the per protocol population).
 - Cohorts 1 and 2 the subjects also minimally completed the 7-day follow-up visit; and

- Cohort 3 the subjects had both complete infusion doses and minimally completed the 7-day follow-up visit after the second infusion.

The demographic tables (Table 1.1- Table 1.20) will include all five analysis populations listed in Section 4.2 unless it is found that both full populations include the same subjects, in which case only one table for the F1 and F2 population will be produced with the title indicating that it represents the F1, F2 populations, unless otherwise specified. Likewise, if all three safety populations are found to include the same subjects, only one table will be produced with the title indicating that it represents all safety populations, the S1, S2 and S3, unless otherwise specified. This pattern of table reduction will be repeated for the remaining tables unless otherwise indicated. Subject disposition tables will include all five populations. AE tables that display overall AE incidence will include all five populations. Tables that are restricted to TEAEs will include the safety populations only. Study drug exposure will be presented in the first safety population (S1). All other analyses will be performed in the third safety population only (S3).

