4.5.3 Conduct Safety Analyses (Primary Objective)

To provide the DSMB with formal safety reports for review, analyses required to generate Table 1.1 – Table 8.3 and Figures 1 and 2 will be conducted as prescribed in the FDP-1 DSMB Charter, except for Tables 7.4-7.6. For Cohort 3, Open and Closed session tables will be created. The Open session tables will present overall totals for Cohort 3. The Closed session tables will present the data by masked treatment arm (A or B).

Safety data will be summarized for each cohort using standard descriptive statistics.

- For quantitative variables, the following statistics will be provided:
 - Number of subjects;
 - Mean;
 - Standard deviation, minimum, maximum;
 - Median; and
 - 25th and 75th percentile.
- For categorical variables, percentages will be calculated using the number of subjects with non-missing data for the specific variable.

AEs will be coded using the most recent version of the Medical Dictionary of Regulatory Activities preferred terms and will be grouped by system, organ, and class designation. AEs will be summarized using standard FDA-recommended templates distinguishing those defined as TEAEs. A TEAE will be defined as an AE that emerges during or following treatment (infusion), having been absent pretreatment. For all TEAEs, relatedness to infused product will be presented. TEAEs related to study treatment will be defined as definitely or probably related to study treatment. A SUSAR will be defined as a Suspected, Unexpected, Serious Adverse Reaction. A listing of SUSARs will be provided by USAMMDA upon reconciliation of their SAE database with the Oracle Clinical database.

Use of the Centers for Disease Control National Healthcare Safety Network Hemovigilance Module criteria will ensure consistent definitions are applied when using transfusion-related event terms, such as

transfusion related acute lung injury or transfusion associated circulatory overload. The National Cancer Institute Common Terminology Criteria will be used to assess all event terms (AEs) for toxicity grade, or severity, regardless of whether the event is transfusion-related (HHS-2010). AEs will also be presented by maximum severity or maximum common terminology criteria for AE (CTCAE) grade (depending on collection). A summary of SAEs and a summary of AEs leading to treatment discontinuation will be presented.

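### Two wordings can modestly undercount non-serious TEAEs: a definition with no worsening clause, and a 24-hour symptom checklist at the day-14 call

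*SAP*

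**What the plan says.** The plan defines a TEAE in five places and in two ways. SAP 4.5.3 says "A TEAE will be defined as an AE that emerges during or following treatment (infusion), having been absent pretreatment", and Protocol 11.1.3 has the same sentence. The other three use timing only: the synopsis ("TEAEs are adverse events (AEs) that occur after administration of the study treatment, plasma infusion, has begun"), Protocol 6.1 ("These are adverse events (AEs) that occur after treatment (plasma infusion) has begun") and SAP Section 2 ("defined as only AEs that occur after starting the trial infusion administration"). None mentions worsening.

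The synopsis gives the definition its weight: "Conclusions on whether the study meets its safety objectives will be based only on treatment emergent adverse events (TEAEs"; Protocol 6.1 says the same. On events before infusion the synopsis adds "AEs occurring prior to treatment (e.g., AEs that occur during autologous plasma collection) will not be considered relevant" to the objectives. SAP Section 2 is broader: "In addition to TEAEs, safety will be evaluated based on the occurrence of SAEs", and also on SUSARs and deaths.

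Protocol 10.5.1 records donation-related events as AEs, and other events between consent and the first infusion visit as medical history. Protocol 10.4 keeps one AE record at the highest severity over continuous days. SAP Listing 17 (AEs before dosing) has one start date and one grade per event.

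For telephone follow-up, Appendix H is one script for the 48-hour, 72-hour and 14-day calls, and its symptom checklist covers the previous 24 hours. Protocol 8.3.2 describes the same questions as reaching back to the infusion visit. Protocol 8.3.4 has the 28-day visit review AEs only since the 14-day call.

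**The concern.** A headache or a bruise from donation that is mild before infusion and moderate after it is not clearly a TEAE. Under SAP 4.5.3 it was not absent before treatment. Under the timing-only wordings it depends on whether the investigator treats the worsening as a new event, and no passage says to do so. It could then be left out of the TEAE tables by term, relatedness and severity (SAP Tables 3 to 6), which are the ones that bear on the stated conclusion.

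The day-14 checklist works in the same direction by another route. Chest pain, breathlessness or calf pain that came and went early in the second week is not asked about by name at that call, and the next visit is not directed to look back that far.

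This is a first-in-human study with 4 subjects per arm, so a single reclassified subject is visible in the arm-level figures.

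**Working it through.** **The plan's own figure.** The only stated statistic on incidence is SAP Table 3. With Clopper-Pearson limits, lower = Beta quantile(0.025; x, n−x+1) and upper = Beta quantile(0.975; x+1, n−x). For n = 24 and x = 24 × 0.10 = 2.4, the limits are 1.61% and 29.19%, width 27.58. The plan gives 1.6 to 29.2, width 27.6. All nine cells reproduce to rounding. This point does not dispute them.

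**Definition, followed through the recording rules.** Take a condition that starts before the first infusion and worsens after it.

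| Route (Protocol 10.5.1) | Record | Where it shows |
|---|---|---|
| Donation-related | One AE record with its pre-infusion start date and highest grade (10.4) | Overall AE rows and Listing 17; not clearly in the TEAE tables |
| Not procedure-related | Medical history | Listing 9 covers screening history and shows a term with no onset date or grade; no passage says whether worsening creates an AE record |

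Listing 17 also shows ongoing status, relatedness, action taken and outcome. It would show that an event was ongoing or judged related, but not that its peak came after infusion. The one passage on progression, Protocol 10.5.2, concerns SAEs and treats progression as follow-up to the original event.

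**How long a donation-related event must last to matter.** Collection is on Day −35 in Cohort 1, Day −63 to −35 in Arm 3, Day −45 to −35 in Arm 4 and Day −55 to −35 in Cohort 3 (Protocol Tables 4, 5, 6 and 8). Infusion is on Day 1. The event must persist for about 35 to 63 days (one more if a Day 0 is counted). A medical-history event can start later, but must then pass the pre-infusion review.

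**Per-subject arithmetic.** One affected subject with no other TEAE is 1/4 = 25% of an arm or 1/24 = 4.2% of the study. This is not an estimate of how often it happens.

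**Checklist coverage.** Inputs: 24-hour visit ±3 h, 48- and 72-hour calls ±2 h, 7-day visit ±1 day, 14-day call ±2 h, recall 24 h. Uncovered time = interval since last contact − 24 h.

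- 24-hour visit to 48-hour call: longest interval (48+2) − (24−3) = 29 h, so at most 5 h uncovered.
- 48-hour to 72-hour call: longest interval (72+2) − (48−2) = 28 h, so at most 4 h uncovered.
- 7-day visit to 14-day call: 14 − 7 = 7 days, range 14 − 8 = 6 to 14 − 6 = 8. Less 1 day of recall: 6 days uncovered, range 5 to 7. As a share, 6/7 = 86% (5/6 = 83% to 7/8 = 87.5%). The ±2 h on the call is ignored.
- Cohort 3 after infusion 2: Day 22 to Day 29 = 7 days, the same result. After infusion 1 there is no 14-day call, and Protocol 8.2.2 has the second infusion visit review AEs since collection.

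The 24-hour recall therefore fits the first two calls and not the third.

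**The case against.** The strongest reply is that little can be lost, and most of it stands.

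- Subjects are healthy volunteers, with most organ-system disease, hypertension and current treatment for infection excluded. History, medications and AEs are reviewed and a complete physical examination is done before infusion, and the PI may withhold the infusion (Protocol 8.2.1, 8.2.2).
- Vital signs and laboratory values are compared with the pre-infusion baseline (Protocol 11.1.1, SAP 4.4.2), so objective worsening appears whatever its TEAE status.
- SAEs, SUSARs and deaths are primary endpoints in their own right, and the stopping rules do not depend on TEAE status.
- Anything recorded as an AE stays in the overall counts: "AE tables that display overall AE incidence will include all five populations".
- At day 14, the script's opening question goes back to the last visit and Protocol 10.5.1 supplies an open question about the time since last contact. Both span the whole week.

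What remains is narrow: non-serious, mostly subjective worsening of an existing complaint, and the loss of prompting by named symptom for most of one week. On the text itself the reply has no answer: no passage counts worsening, and Appendix H and Protocol 8.3.2 disagree.

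Three stronger readings may tempt a reader. The first is that 6 of 7 days means most AEs in that week are missed. It does not; it counts days of prompted recall. The second is that thromboembolic symptoms go unwatched once the last scheduled Wells assessment is done at 24 hours. Protocol 10.5.1 calls for a focused review of systems and examination for coagulation disturbance, examinations follow at 7 and 28 days, and DVT, PE and cardiac ischemia are stopping events. The third is that escalation could go wrong because the synopsis names absence of TEAEs as a condition. The DSMB reviews the safety data and recommends, and the sponsor decides.

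**Conclusion.** The point holds as a minor one. The plan uses two TEAE definitions, neither of which counts worsening of a condition present before the first infusion, and the day-14 checklist does not fit its interval. Both can only lower the TEAE count.

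The size of the undercount cannot be computed. The documents give no rate of conditions present at infusion, no rate of worsening, and no share of symptoms that unprompted questions would miss. Any assumed share would yield a figure resting wholly on that assumption. What can be stated is the 5 to 7 days without prompted recall, and the judgement that cases under the definition are probably few. That judgement rests on the healthy population, the roughly 5-week gap from collection to infusion, and the pre-infusion examination being done as written.

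In Cohort 3, an event that begins after infusion 1 and worsens after infusion 2 is already a TEAE when pretreatment is read as before the first infusion. Only its attribution to a product is open, and SAP 4.5.3.1 already covers that.

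**What to change.** 1. Put one definition in the synopsis, Protocol 6.1 and 11.1.3, and SAP 2 and 4.5.3: an AE with onset at or after the start of the first infusion, or an AE or medical-history condition present before the first infusion that increases in severity at or after its start.
2. For those pre-first-infusion conditions only, add to Protocol 10.4 and 10.5.1 that the increase is entered as a new AE record with its own start date and grade. Keep the single-record rule for ordinary TEAEs; otherwise every event that rises in grade would be split. Leave Cohort 3 attribution of events that began after infusion 1 to SAP 4.5.3.1 and its exceptions, so that one continuing event is not placed under both products.
3. In Appendix H, make the checklist recall at the day-14 call 'since your last visit or call'. That closes the gap and brings the script closer to Protocol 8.3.2.

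The cost is wording in two documents, one eCRF rule, a small change to the TEAE derivation and one script line. No visit or test is added. TEAE counts may be slightly higher, and a few pre-existing events will have two records.

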4.5.3.1 Primary Safety Endpoints

The primary safety endpoints to be assessed are AEs, specifically:

- TEAEs;
- SAEs;
- SUSARs; and
- Deaths.

Descriptive statistics will be used to analyze the primary safety endpoints. Tables produced to exhibit the primary safety endpoint data will be presented by the specific type of plasma product infused. In Cohorts 1 and 2, this data will be presented by FDP product type, FDP-ACD and FDP-CPD; in Cohort 3 by experimental product and control product, FDP and FFP. The primary safety data reported to the DSMB for Cohort 3 will be masked. Unblinding during the study will only occur in accordance with Section 3.3.2 following Westat's SOP DA-504 Development of a Plan for Randomization, Masking, and Unmasking.

In general, AEs that occur in Cohort 3 subjects within 14 days after infusion will be attributed to the most recently infused product. However, there may be exceptions to use of this temporal attribution rule to all transfusion-related AEs given the possibility that those AEs that occur after infusion with the second product may potentially be related to infusion with the first infusion product (e.g., an immunogenic response).

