## 6.8. Duration of Subject Participation

Subjects in Cohort 1 will complete the study in approximately 3 months. Subjects in Cohort 2, Arm 3 will complete the study in approximately 4 months; subjects in Cohort 2, Arm 4 will require approximately 3 months. Subjects in Cohort 3 will complete the study in approximately 4 months. The first infusion for all cohorts is defined as Study Day 1. Study Day 15 is the second infusion for Cohort 3. The manufacturing time is currently estimated to be 5 weeks and although accounted for in study participation time, no subject activities are planned during this time. Screening and baseline assessment and informed consent visits will require approximately 2 hours. Final eligibility assessments and WB collection or plasmapheresis will require approximately 4 hours. On the day of infusion, the infusion and post-infusion studies will require approximately 8 hours.

For all cohorts, the on-site follow-up assessments will take 1 to 2 hours to complete, and the telephone assessments will take 15 to 20 minutes to complete. Cohorts 1 and 2 will have on-site follow-up assessments on Study Days 2, 8, and 29 and telephone follow-up assessments on Study Days 3, 4, and 15. Cohort 3 will have on-site follow-up assessments on Study Days 2, 8, 16, 22, and 43 and telephone follow-up assessments on Study Days 3, 4, 17, 18, and 29.

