### 8.3.4. 28-Day Follow-Up Visit

A post-infusion follow-up visit will be scheduled 28 days ( $\pm$  1 day) post-infusion for subjects enrolled in Cohorts 1 and 2. For subjects enrolled in Cohort 3, a 28-day post-infusion follow-up visit will take place after the second plasma infusion, only, approximately 42 days after the first infusion visit. The following procedures will be performed at these follow-up visits:

- Review of medical history, concomitant medications, and AEs since the 14-day telephone follow-up contact;
- Abbreviated physical exam which includes vital signs (blood pressure, heart rate, respiration rate, and temperature) and a general assessment of health;
- Collect blood samples as noted for all tests listed in the Schedule of Events tables (Table 4, Table 5, Table 6, and Table 8); and
- Exit interview concluding the subject's study participation.

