2.2.3 Infusion Visit(s)

The infusion visit for the first subject in each cohort is to occur approximately five weeks following his or her last collection visit. Unlike Cohorts 1 and 2 subjects, Cohort 3 subjects require two infusion visits. These are to occur with no less than a two-week interval in between infusions. Subjects will undergo autologous infusion at each of these visits according to the corresponding treatment specifications of the arm to which they belong.

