2.2.4 Follow-up Visits

Post-infusion, subject assessments are to occur at scheduled in-person and telephone follow-up visits. For Cohorts 1 and 2, in-person post-infusion visits will occur on Study Days 2, 8, and 29, which corresponds to conducting assessments 24 hours, 7 days, and 28 days post-infusion. These visits will take one to two hours. Telephone follow-up visits of a 15 to 20 minute duration are to occur on Study Days 3, 4 and 15, or 48 hours, 72 hours, and 14 days post-infusion.

Follow-up visits for Cohort 3 subjects subsequent to the first infusion visit are the same as those scheduled for Cohorts 1 and 2. However, on Study Day 15, Cohort 3 subjects will undergo the second infusion and accompanying follow-up visits for this infusion are spaced in time to occur as those performed for Cohorts 1 and 2. Cohort 3 in-person follow-up visits will be scheduled for Study Days 2, 8, 16, 22, and 43 and take 1 to 2 hours to complete. The telephone follow-up visits, each taking approximately 15 to 20 minutes to complete, will be conducted on Study Days 3, 4, 17, 18, and 29.

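### Cohort 3 adverse events starting more than 14 days after an infusion have no assigned product, so the promised by-product TEAE counts are incomplete

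*SAP*

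**What the plan says.** **The rule.** SAP 4.5.3.1, repeated in protocol 11.1.1, states as a general rule that "AEs that occur in Cohort 3 subjects within 14 days after infusion will be attributed to the most recently infused product". It then adds that "there may be exceptions to use of this temporal attribution rule to all transfusion-related AEs", because an event after the second infusion might stem from the first product. Neither text covers an event that starts more than 14 days after an infusion.

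**The schedule.** Protocol 6.8 states that "Study Day 15 is the second infusion for Cohort 3". SAP 2.2.4 states that "Cohort 3 in-person follow-up visits will be scheduled for Study Days 2, 8, 16, 22, and 43". Under protocol 8.3.4 the 28-day visit "will take place after the second plasma infusion, only, approximately 42 days after the first infusion visit", and AEs since the 14-day call are reviewed there. Protocol Table 8 also schedules CBC, PT/INR, aPTT and DAT at that visit.

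**What counts, and where it is shown.** The TEAE definition in SAP 4.5.3 has no end date, and protocol 6.1 counts TEAEs over the whole post-infusion follow-up. SAP 4.5.3.1 promises the Cohort 3 primary safety tables by product, FDP and FFP. The final Cohort 3 columns in the AE shells (SAP section 5, Tables 2 to 8) are by sequence instead.

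**The concern.** The attribution rule is the only device in the SAP that turns a Cohort 3 adverse event into an FDP event or an FFP event. It stops at 14 days, but AE collection does not. An event reported for the first time at the Day 43 visit, or found in the blood drawn there, is a TEAE with no product under the rule as written.

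TEAEs are a primary endpoint and, by protocol 6.1, the sole basis for the safety conclusion. The plan itself allows for delayed effects: SAP 4.5.3.1 gives an immunogenic response as its example, and the worksheet in protocol Appendix I lists delayed hemolytic and delayed serologic transfusion reactions. With eight subjects, one event left out or placed by judgement can change a by-product row visibly.

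The exceptions clause does not close the gap. It concerns events after infusion 2 that may belong to the first product, and it gives no criteria, no decision-maker and no requirement that the decision precede unblinding.

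**Working it through.** **Inputs**
- Attribution window: 14 days after each infusion (SAP 4.5.3.1, protocol 11.1.1).
- Infusion 1 on Study Day 1 and infusion 2 on Study Day 15 (protocol 6.8).
- Last visit 28 days after infusion 2 (protocol 8.3.4, SAP 2.2.4).
- Window for infusion 2: ± 3 days (protocol Table 8).
- Four subjects per sequence, eight in all (SAP Table 1), with replacement in the same arm (SAP 3.4).
- End of AE collection: seven days after the last required sample, with Day 29 given in brackets (protocol 10.5.1).

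**Step 1. Reproduce the schedule.** 1 + 14 + 28 = Study Day 43, which is 14 + 28 = 42 days after infusion 1. This agrees with protocol 8.3.4.

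**Step 2. Size of the gap, infusion 2 on Day 15.** The second window closes on Study Day 15 + 14 = 29. Days after that have no product. Protocol 10.5.1 does not fit Cohort 3 cleanly, because the last Cohort 3 sample is on Day 43, not Day 29. Three readings follow:

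| End of AE collection | Unassigned days per subject | Post-infusion days per subject | Subject-days (8 subjects) | Share |
|---|---|---|---|---|
| Day 29 + 7 = Day 36 | 36 - 29 = 7 | 14 + 21 = 35 | 56 of 280 | 20% |
| Day 43 visit | 43 - 29 = 14 | 14 + 28 = 42 | 112 of 336 | 33.3% |
| Day 43 + 7 = Day 50 | 50 - 29 = 21 | 14 + 35 = 49 | 168 of 392 | 42.9% |

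**Step 3. Late infusion 2.** If every infusion 2 fell on Day 18, 17 - 14 = 3 further days per subject would be uncovered before it. With a last visit 28 days later, this gives 8 × (3 + 14) = 136 of 8 × (17 + 28) = 360 subject-days, or 37.8%. The early side of the window is not used here, because it conflicts with SAP 2.2.3, which says of the infusion visits: "These are to occur with no less than a two-week interval in between infusions".

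**Step 4. Follow-up by product and by infusion, Day 43 end.**
- With the 14-day cap: FDP = 4 × 14 + 4 × 14 = 112 subject-days; FFP = 112.
- Without the cap: FDP = 4 × 14 + 4 × 28 = 168; FFP = 4 × 28 + 4 × 14 = 168.
- By infusion, without the cap: infusion 1 = 8 × 14 = 112; infusion 2 = 8 × 28 = 224.

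Follow-up is thus unequal between infusions within a subject (14 against 28 days), but equal between products.

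**Step 5. Illustration in events.** Assume a constant risk and a 14-day risk p of having an event. The 28-day risk is 1 - (1 - p)². Expected subjects with an event, per product, are 4p + 4[1 - (1 - p)²] over full follow-up and 8p under the rule.

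| p (assumed) | Full follow-up | 14-day rule | Missed, each product |
|---|---|---|---|
| 5% | 0.59 | 0.40 | 0.19 |
| 10% | 1.16 | 0.80 | 0.36 |
| 25% | 2.75 | 2.00 | 0.75 |

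**Step 6. When products could differ.** Population S1 keeps anyone who received any volume, and dropouts are replaced in the same arm. One extra Arm 5 subject who leaves 14 days after infusion 1 gives FDP 112 + 14 = 126 against FFP 112 with the cap, or 182 against 168 without it.

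**The case against.** The best reply is that the rule is stated only as a general one, that the most recently infused product plainly remains so until Day 43, and that no specified table loses an event. Much of this stands. Late events stay in every Cohort 3 total and by-sequence count, and Listing 13 gives onset dates. The analysis is descriptive, with no test (protocol 11.3). Acute infusion reactions come early, and only one contact is scheduled after Day 29, so the share of events affected may be well below the share of days.

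The reply does not remove the gap. The text limits attribution to 14 days, and if the last product is meant to carry on, the SAP should say so. The absence of by-product tables is a further conflict with SAP 4.5.3.1: Listing 13 has no product or infusion-number column, so a reader would have to rebuild product from arm and infusion dates.

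A reader might infer three stronger points that the documents do not support:
- **That FDP and FFP are followed for unequal times.** Step 4 shows equal totals with balanced sequences, capped or not. A difference needs an unbalanced S1, as in step 6.
- **That secondary objective 1 rests on this rule.** Protocol 11.1.2.1 and SAP 4.5.4 base that analysis on changes from baseline in the measures of protocol Table 15 and SAP Table 5.
- **That exceptions will be decided with product known.** The investigator and the treating staff are blinded, and general unblinding follows database lock. The fair criticism is only that the SAP does not fix who decides, or when.

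**Conclusion.** The concern holds in this form: Cohort 3 TEAEs that start more than 14 days after infusion 2, or between day 14 and a late infusion 2, have no product under the written rule. The by-product counts that SAP 4.5.3.1 promises for a primary endpoint are incomplete to that extent.

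The gap is 33% of post-infusion subject-days if AE collection ends on Day 43, and 20% to 43% across the readings of protocol 10.5.1 with infusion 2 on Day 15. These are shares of time; the documents give no event rates by day. Under balanced sequences and constant risk the loss is the same for both products, so the defect is incompleteness rather than a bias toward one product. It should be corrected before unblinding, but it does not affect the Cohort 3 totals or by-sequence counts.

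**What to change.** 1. Attribute every Cohort 3 TEAE to the most recently started infusion until the next infusion or the end of follow-up.
2. Use infusion start to 14 days, or to the next infusion if earlier, as the like-for-like FDP versus FFP window.
3. Tabulate later events separately, by last product and period.
4. Decide and document attribution exceptions before unblinding, and show counts with and without them.
5. Add product columns to the Cohort 3 AE tables, whose shells are now by sequence only.
6. Reconcile the end of AE collection in protocol 10.5.1 with the Day 43 visit, and the ± 3-day window for infusion 2 with the stated minimum interval.

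The cost is SAP wording, one derived variable and added product columns across the Cohort 3 AE tables. Because the rule also stands in protocol 11.1.1, protocol 11.6 calls for the change to be described in both documents. No new data and no change to treatment are needed.
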